9.3.2. Safety Analysis Populations

The Safety Analysis Set - Extension (SAF-Ext) population will be used to for the analysis of safety data in this study.

The SAF-Ext consists of all randomized subjects in Study URO-901-3005 who

- a) have completed the 24-week treatment period in the Study URO-901-3005, and
- b) enrolled into the extension Study URO-901-3006 and received at least one dose of vibegron in this study.

The SAF-Ext will be used for all the safety analyses. Safety endpoints will be descriptively summarized based on the treatment in study URO-901-3006. This means there will be one vibegron treatment group (combining 52 weeks of vibegron dosing for those continuing vibegron from Study URO-901-3005 and 28 weeks of vibegron dosing for those who received placebo in Study URO-901-3005).

No imputation will be performed for missing safety data. Baseline will be the same as the baseline defined in the parent study. Further inclusion of data from URO-901-3005 in the reporting of this study will be described in the SAP.

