1.1. Study Objectives and Endpoints

Assessments in Study URO-901-3006 are referenced to the initial Baseline (Visit 3) from Study URO-901-3005. Change from baseline (CFB) study endpoints for safety parameters for study URO-901-3006 are relative to the most recent assessment prior to starting vibegron. CFB study endpoints for efficacy in Study URO-901-3006 are relative to Study URO-901-3005 baseline. At the Week 52 visit, CFB comprises 52 weeks of vibegron exposure for subjects randomized to vibegron in Study URO-901-3005 and 28 weeks of vibegron exposure for subjects randomized to placebo.

With respect to study endpoints, “per day” refers to a “Diary Day”, which is defined as the time between when the subject gets up for the day each morning and the time the subject gets up for the day the next morning as recorded in the subject bladder diary (approximately a 24-hour period).

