3.1.2. Safety Analysis Set Extension

The Safety Analysis Set Extension (SAF-Ext) will serve as the primary population for the analysis of safety data in this trial.

The SAF-Ext consists of all randomized subjects in Study URO-901-3005 who

- a) have completed the 24-week treatment period in the Study URO-901-3005, and
- b) enrolled into the extension Study URO-901-3006 and received at least one dose of vibegron in this study.

Safety endpoints will be descriptively summarized for the entire Safety Analysis Set Extension. No imputation will be performed for missing safety data. Baseline will be established as the last observation prior to the first dose of vibegron. All safety data collected on or after the first exposure to vibegron within the combined experience of the patient on URO-901-3005 and

URO-901-3006 will be included in the safety analysis for URO-901-3006, and all analyses by visit will index visits from the first dose of vibegron on either study; subjects who received placebo in study URO-901-3005 will only contribute safety data up to Week 28.

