2. For non-early withdrawal records, if a nominal visit number for a scheduled visit was assigned, then it will be used to summarize the record after checking to make sure that visit numbers match with therapy phases:

- Check that all records entered as a pre-treatment visit for study URO-901-3005 occur on or before the day of the first dose of double-blind treatment (i.e. day ≤1). Any record with day > 1 should be re-slotted to an on-treatment visit using the relative day window below.
- Check that all records slotted to an on-treatment visit for study URO-901-3005 and all records for study URO-901-3006 are on or after the day of the first dose of double-blind treatment. If they are not, the visit should be moved to pre-treatment.

3. Any early withdrawal record (regardless of the visit number assigned), any unscheduled visit record at any time, any repeat visit record, or any record for which the visit number was missing or the visit number was not for a scheduled visit, should be slotted or re-slotted to a visit using the window below.

Table 4: Analysis Visit Window Slotting

Analysis window label	URO-901-3005 Randomized Arm					
	Vibegron			Placebo		
	Nominal visit	Nominal day	Visit Window	Nominal visit	Nominal day	Visit Window
Baseline	Visit 3	1	NA ^a	Visit 3	1	[1,182 ^b]
Week 1	Visit 4	8	[2, 11]	NA	NA	NA
Week 2	Visit 5	15	[12, 22]	NA	NA	NA
Week 4	Visit 6	29	[23, 42]	Visit 12	197	[183 ^c ,224]
Week 8	Visit 7	57	[43, 70]	NA	NA	NA
Week 12	Visit 8	85	[71, 98]	Visit 13	253	[225,308]
Week 16	Visit 9	113	[99, 126]	NA	NA	NA
Week 20	Visit 10	141	[127, 154]	NA	NA	NA
Week 24	Visit 11	169	[155, 182 ^a]	NA	NA	NA
Week 28	Visit 12	197	[183 ^b , 224]	Visit 14	365	> Day 309
Week 36	Visit 13	253	[225, 308]	NA	NA	NA
Week 52	Visit 14	365	> Day 309	NA	NA	NA

a Must have occurred prior to the first dose administered in study URO-901-3005.

b Must have occurred prior to the date of first dose administered in study URO-901-3006.

c Must have occurred on or after the date of first dose administered in study URO-901-3006.

Note: The cut-off days to define the window for slotting through Week 20 are aligned with study URO-901-3005.

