For parameters which were **not** scheduled to be collected at all visits, the all-inclusive visit intervals defined for all visits (i.e., the window defined above) will still be used to slot records. If a value is slotted to a visit unscheduled for a parameter, it will not be summarized (and not be included in the efficacy datasets) but will be included in data listings.

4. If after all records have been slotted or re-slotted, there are multiple valid records within a visit, use the record following the rules below:
 - If there are multiple values for an endpoint in one window, the visit closest to the nominal day will be selected for by-visit displays. If the visits are equidistant from the nominal day, then the earlier visit will be selected. All values will be stored in analysis datasets.

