4.3.4. Baseline and Change from Baseline

In general, the last recorded value on or prior to the date of randomization in the parent study URO-901-3005 will serve as the baseline measurement for efficacy endpoints while the last recorded value prior to first double-blind dose of study treatment will serve as the baseline measurement for safety endpoints. The mean of multiple values will be used as baseline for the following situations:

- If multiple measurements are scheduled on the same baseline day (i.e., blood pressure)
- If multiple measurements are collected on the same baseline day without the time or “repeat” status to differentiate the records

For efficacy endpoints derived from the Bladder Diary, the baseline will be the average value over the diary days in the baseline analysis visit window on study URO-901-3005.

Change from baseline will be calculated as the post-baseline value minus the baseline value. Percentage change from baseline will be calculated as the change from baseline divided by the baseline value, multiplied by 100. If either the baseline or post-baseline value is missing, then change from baseline and percentage change from baseline will be set to missing.

5. Demographics, Other Baseline Characteristics, Procedures And Medication

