7.5. Vital Sign Assessments

Vital sign data including blood pressure, pulse rate, respiration rate, body temperature and weight will be collected at all study visits except for the Week 1, Week 16, and 44 telephone visits. Height will be measured at Screening only. Blood pressure will be measured in triplicate at each visit. The average of triplicates will be used for summary. For subjects in URO-901-3005 Study Part 1 at any visits with orthostatic blood pressure measurements: blood pressure (in triplicate) and pulse rate taken pre-dose in sitting position are equivalent to all other pre-dose vital sign values and will be used. Orthostatic and standing blood pressure measurements collected during Part 1 of URO-901-3005 will not be included in any summaries on URO-901-3006.

For all parameters, absolute values and change from baseline will be presented for scheduled visits using descriptive statistics for continuous variables. In addition, the maximum post-baseline change from baseline value and change from baseline to the end of treatment will be summarized for each of the vital signs.

To further investigate changes in SBP/DBP/pulse rate from baseline, the following tables will be prepared:

- Counts and percent of subjects in each group with at least a 5/10/15 CFB at 2 consecutive post-baseline visits and at Week 52 will be produced for all subjects, by pre-existing hypertension category (Yes/No) and by pre-existing hypertension category (Yes/No).
- Maximum post-baseline CFB (including 95% CI of Mean)

The line plot of mean (SE) of change from baseline in blood pressure and pulse rate over time will be prepared. A by-subject listing, sorted by subject identifier, will be presented including all vital sign results (scheduled or unscheduled).

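### SAP 4.3.4 sets the safety baseline before the first double-blind dose while SAP 1.1 and 3.1.2 set it before first vibegron, and the blood-pressure run in SAP 7.5 is 2 visits in the text but 3 in its table title

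*SAP*

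**What the plan says.** **Baseline.** SAP 4.3.4, the section that defines baseline, says that, in general, "the last recorded value prior to first double-blind dose of study treatment will serve as the baseline measurement for safety endpoints". SAP 1.1 says that safety changes are "relative to the most recent assessment prior to starting vibegron". SAP 3.1.2 says "Baseline will be established as the last observation prior to the first dose of vibegron". In SAP Table 4 the baseline window for the placebo arm runs from Day 1 to Day 182, with a footnote: "Must have occurred prior to the date of first dose administered in study URO-901-3006". The nominal visit printed beside that window is Visit 3, Day 1. SAP 7.5 speaks only of baseline and does not choose.

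Protocol 9.3.2 says, for safety: "Baseline will be the same as the baseline defined in the parent study". SAP 9, which lists changes from the protocol, has four entries: the wording of the IPSS storage endpoint, added exploratory timepoints, COVID-19, and physical examination. None concerns the safety baseline.

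**Run length.** SAP 7.5 asks for "Counts and percent of subjects in each group with at least a 5/10/15 CFB at 2 consecutive post-baseline visits", and for the same counts at Week 52. In SAP 11.1.1, Table 14.3.4.2 is titled for shifts at three consecutive visits. No other listed table covers the two-visit analysis.

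**Two smaller slips in SAP 7.5.** The subgroup by pre-existing hypertension is named twice. The Week 52 count is requested for each group, although SAP 3.1.2 says that "subjects who received placebo in study URO-901-3005 will only contribute safety data up to Week 28".

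**The concern.** Vital signs, laboratory values, PVR and Total IPSS are all listed under the primary objective in SAP 1.1.1. For men randomized to vibegron in the parent study the two baseline rules coincide. For former-placebo men they lie about 24 weeks apart. Under 4.3.4 their tabulated change on vibegron would be the true on-vibegron change plus whatever happened during 24 weeks of placebo. The Overall column would mix the two kinds of change.

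Two careful programmers could therefore produce different 28-week and Overall columns from the same SAP, and different counts in Table 14.3.4.2. If the choice is made after the parent study is unblinded, it has to be explained. A correction made beforehand does not.

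**Working it through.** The plan gives no figure on this point, so there is none to reproduce. The check traces each rule through the text and then sizes the consequences.

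**1. Which baseline each place gives a former-placebo man**

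| Place | Safety baseline |
|---|---|
| SAP 4.3.4 | Day 1 of URO-901-3005 |
| SAP 1.1 | last value before first vibegron, about Week 24 |
| SAP 3.1.2 | last value before first vibegron, about Week 24 |
| SAP Table 4, window and footnote b | any value up to the first URO-901-3006 dose; fits 3.1.2 |
| SAP Table 4, nominal visit | Visit 3, Day 1; does not match its own window |
| Protocol 9.3.2 | parent-study baseline |

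**2. Effect on mean change.** Write the change at time t under 4.3.4 as

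Y(t) − Y(Day 1) = [Y(t) − Y(Week 24)] + [Y(Week 24) − Y(Day 1)].

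The first bracket is the change under 3.1.2. The second has mean d, the change over the placebo period. The 28-week group mean therefore differs by exactly d between the rules. With equal groups the Overall mean differs by d/2. Equal groups of about 150 of 300 are inferred from the sample-size text: 150 × (1 − 0.33) = 100.5, against the 100 one-year completers stated there.

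**3. Readings available.** SAP 7.5 excludes the Week 1, 16 and 44 telephone contacts. With Table 4, this leaves:

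- 52-week group: Weeks 2, 4, 8, 12, 20, 24, 28, 36 and 52. That is 9 readings, 8 possible pairs and 7 runs of three.
- 28-week group: treatment Weeks 4, 12 and 28 (Visits 12, 13 and 14). That is 3 readings, 2 possible pairs and 1 run of three.

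**4. Run length, 28-week group.** Assumed, not in the documents: each systolic reading is the man's true level plus independent normal error with SD s = 6, 8 or 10 mmHg, and there is no drug effect. The change is e_i − e_0, so the true level cancels. Given e_0, a reading exceeds threshold c with probability p = 1 − Φ((c + e_0)/s). Then

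- at least 2 consecutive of 3: 2p² − p³
- all 3: p³

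each averaged over e_0 ~ N(0, s²).

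| Rise of at least | 2 visits (s = 6 / 8 / 10) | 3 visits | Ratio 3:2 |
|---|---|---|---|
| 5 mmHg | 19.2 / 24.1 / 27.3% | 8.8 / 11.9 / 14.0% | 0.46 / 0.49 / 0.51 |
| 10 mmHg | 6.2 / 11.5 / 15.8% | 2.1 / 4.5 / 6.8% | 0.34 / 0.39 / 0.43 |
| 15 mmHg | 1.4 / 4.4 / 8.0% | 0.3 / 1.4 / 2.9% | 0.24 / 0.31 / 0.36 |

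Ratios are from unrounded values. For comparison, the 52-week group by simulation under the same model, rise of at least 10 mmHg: 15.0 / 25.1 / 32.6% at two visits against 6.5 / 12.6 / 17.8% at three.

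**5. Baseline, 28-week group, rise of at least 10 mmHg at 2 visits.** With a placebo-period shift d, the 4.3.4 rule replaces p by 1 − Φ((c + e_0 − d)/s). The 3.1.2 result does not depend on d. The shifts of −3 and +3 mmHg are assumed.

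| Baseline rule | s = 6 | s = 8 | s = 10 |
|---|---|---|---|
| 3.1.2, any d | 6.2% | 11.5% | 15.8% |
| 4.3.4, d = −3 mmHg | 2.6% | 6.7% | 10.7% |
| 4.3.4, d = 0 | 6.2% | 11.5% | 15.8% |
| 4.3.4, d = +3 mmHg | 12.8% | 18.3% | 22.3% |

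With d = 0 the expected percentage is the same under both rules, but about 10, 17 and 22% of men (s = 6, 8, 10) are counted under one baseline and not the other.

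**The case against.** The intent on baseline is fairly clear. SAP 1.1, SAP 3.1.2 and the Table 4 window agree. SAP Table 2 and the medical-history rule also use first vibegron as the dividing line. SAP 4.3.4 opens with a general qualifier and reads like text carried over from the parent study. The three-visit wording is only in a table title, while both the methods text and the hypertension definition in Protocol 8.4.6 use two consecutive visits. The repeated subgroup is clerical, since SAP 7.3 pairs pre-existing with baseline hypertension. No inferential testing is planned on safety data, and all vital signs are listed by subject, so either rule can be recomputed. All of this stands. It makes the correction easy, but the section that defines baseline still states the other rule.

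Some stronger readings are tempting and are not supported:

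- *Table 4 itself selects Day 1 as the baseline.* Its nominal visit is Visit 3, and the slotting rule for multiple records says "the visit closest to the nominal day will be selected for by-visit displays". That rule governs by-visit displays, whereas SAP 3.1.2 defines the reference for change. The window and its footnote mainly support the before-vibegron rule; the nominal visit is a mismatch to tidy.
- *Former-placebo men have no Week 52 reading.* They do: Visit 14, Day 365, which Table 4 labels Week 28. SAP 6.2.2.3 equates the two for the PGI. The fault is in the label.
- *Hypertension events are being missed, so a table of men meeting the Protocol 8.4.6 thresholds is needed.* Site entry of adverse events is the protocol's mechanism, and nothing in the documents shows under-reporting.
- *The baseline-hypertension subgroup changes too.* SAP 5.2 does not say which baseline it uses, so this cannot be asserted.

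**Conclusion.** The inconsistency is real and worth a minor correction. As written, SAP 4.3.4 gives former-placebo men a change on vibegron that includes the placebo period. This affects the 28-week group and the Overall column only. The size is exactly d in the 28-week mean and d/2 in the Overall mean if the groups are equal; the documents do not give d. The departure of SAP 1.1 and 3.1.2 from Protocol 9.3.2 is not recorded. That protocol section leaves further use of parent-study data to the SAP, but it fixes the baseline itself.

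The two-or-three discrepancy matters most in the 28-week group, where a run of three requires every planned reading to qualify: the three-visit count would be 24 to 51% of the two-visit count. In absolute terms the low end is small: at 15 mmHg and SD 6, about 2 men against 0.5 of an assumed 150 (150 × 1.4% = 2.1; 150 × 0.3% = 0.45).

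All percentages rest on assumed SDs of 6 to 10 mmHg, independent errors, no drug effect and, for the baseline comparison, assumed shifts. Diastolic pressure and pulse were not modelled. The textual conflict depends on none of these.

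**What to change.** 1. In SAP 4.3.4, define the safety baseline as the last value before the first dose of vibegron in either study. In the placebo column of Table 4, change the baseline nominal visit to Visit 11, Day 169, so that it matches its window.
2. In SAP 9, record that the safety baseline departs from Protocol 9.3.2, and why. Add a footnote to the safety tables that efficacy endpoints and the Protocol 8.4.6 hypertension definition keep the URO-901-3005 baseline.
3. Retitle Table 14.3.4.2 for two consecutive visits.
4. Clean-up in SAP 7.5: make the second subgroup baseline hypertension, and label the Week 52 count as treatment Week 28 (Visit 14, Day 365) for former-placebo men.

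The cost is a few text edits before the final programs are settled, with no new data and no additional analysis. The one drawback is that former-placebo men then have a safety baseline different from their efficacy baseline and from the one in the hypertension definition. The footnote in item 2 covers this.

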4.2. General Data Handling Conventions

4.2.1. Study Treatment Description

Treatment groups based on the randomized treatment in the parent study will be displayed as shown in the following table:

Table 1: Study Treatment Description

Data Displays for Reporting		
Description	Sections Included	Order in TLF
52 weeks Vibegron 75mg	Demographic and baseline data, Efficacy, Safety	1

28 weeks Vibegron 75mg	Demographic and baseline data, Efficacy (descriptive tables only), Safety	2
Overall Vibegron 75 mg	Demographic and baseline data, Safety	3

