4.2.4.2. Analysis Visit Windows

Analysis visit windows for both diary and non-diary efficacy data are shown in Table 3. All observations will be given an analysis visit, assigned based on relative study day from the first blinded treatment in study URO-901-3005. If multiple repeats of the same assessment are observed within an analysis window, unless the measure was intended to be averaged over replicates, the record closest to the nominal time (earlier in case of a tie) will be used for by-visit summaries. If fewer than three of the diary days are within the analysis window, only the data within the window will be used to calculate visit-level averages.

Table 3: Efficacy Analysis Visit Window Slotting

Analysis window label	Non-diary data			Diary data		
	Nominal visit	Nominal day	Visit Window	Nominal visit ^a	Nominal day	Window
Baseline	Visit 3	1	NA ^b	Run-in	-1	[-7 ^c , -1]
Week 1	Visit 4	8	[2, 11]			
Week 2	Visit 5	15	[12, 22]	Visit 4	15	[7,18]
Week 4	Visit 6	29	[23, 42]	Visit 5	29	[19, 39]
Week 8	Visit 7	57	[43, 70]	Visit 6	57	[47, 67]
Week 12	Visit 8	85	[71, 98]	Visit 7	85	[68, 102]
Week 16	Visit 9	113	[99, 126]	Visit 8	113	[103, 123]
Week 20	Visit 10	141	[127, 154]	Visit 9	141	[131, 151]
Week 24	Visit 11	169	[155, 182 ^b]	Visit 10	169	[159, 179]
Week 28	Visit 12	197	[183 ^d , 224]	Visit 11	197	[187, 207]
Week 36	Visit 13	253	[225, 308]	Visit 12	253	[243, 263]
Week 52	Visit 14	365	> Day 309	Visit 13	365	[345, 385]

a Nominal visit for diary data is the visit where the diary was dispensed.

b Must have occurred prior to the first dose administered in study URO-901-3006.

c If randomization was delayed for any reason, diaries completed within 7 days prior to the baseline visit will still be considered within the analysis window.

d Must have occurred on or after the first dose administered in study URO-901-3006.

For all non-diary safety data including safety laboratory, vital signs, and PVR volume to be summarized by visit, data records will be slotted to one of the protocol-specified visits using the following algorithm:

1. Determine relative study day and last dose day:

Relative study day will be derived as described in Section 4.3.3.

Note that the date of first double-blind dose on URO-901-3005 is Day 1 and the day before the date of double-blind first dose is Day -1. There is no Study Day 0.

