7.8. IPSS Total Score

IPSS total score at Screening, Day 1, Weeks 4, 8, 12, 24, 36, and 52 for the 52-week treatment group and baseline, Week 12 and Week 28 for the 28-week treatment group will be summarized by treatment group and visit, including change from baseline.

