14.3.2.16	Hypertension Treatment Emergent Adverse Events by Preferred Term, and Baseline Hypertension	SAF-Ext	Descending frequency of preferred term
14.3.2.17	Listing of Deaths	SAF-Ext	

Title		Population	Programming notes
14.3.2.18	Listing of Treatment Emergent Serious Adverse Events	SAF-Ext	
14.3.2.19	Listing of Treatment Emergent Adverse Events Leading to Withdrawal or Interruption of Study Treatment	SAF-Ext	
14.3.2.20	Listing of TEAEs of Special Interest	SAF-Ext	
Safety Labs			
14.3.3.1	Hematology Laboratory Parameters	SAF-Ext	Include observed and CFB
14.3.3.2	Clinical Chemistry Laboratory Parameters	SAF-Ext	Include observed and CFB
14.3.3.3	Urinalysis Laboratory Parameters	SAF-Ext	Include observed and CFB
14.3.3.4	Summary of Other Laboratory Parameters	SAF-Ext	
14.3.3.5	Abnormal Classification of Hematology Laboratory Parameters	SAF-Ext	
14.3.3.6	Abnormal Classification of Clinical Chemistry Laboratory Parameters	SAF-Ext	
14.3.3.7	Abnormal Classification of Urinalysis Laboratory Parameters	SAF-Ext	
14.3.3.8	Abnormal Classification Summary of Other Laboratory Parameters	SAF-Ext	
14.3.3.9	Shift Table of L/N/H Classification for Hematology Laboratory Parameters	SAF-Ext	
14.3.3.10	Shift Table of L/N/H Classification for Chemistry Laboratory Parameters	SAF-Ext	
14.3.3.11	Maximum Post-baseline ALT and AST vs. Maximum Post-baseline Bilirubin	SAF-Ext	

Title		Population	Programming notes
14.3.3.12	Listing of Subjects who Potentially Met Hy’s Law	SAF-Ext	
14.3.3.13	Summary of Liver Function Laboratory Findings	SAF-Ext	
Vital Signs			
14.3.4.1	Vital Sign Parameters	SAF-Ext	Include all observed and CFB
14.3.4.2	Vital Sign Parameter Change from Baseline Shifts at 3 Consecutive Visits	SAF-Ext	SBP, DBP and PR
14.3.4.3	Vital Sign Parameter Change from Baseline Shifts at Week 52	SAF-Ext	SBP, DBP and PR
14.3.4.4	Vital Sign Parameter Maximum Post-Baseline Change from Baseline	SAF-Ext	SBP, DBP and PR
Other			
14.3.5.1	Post-Void Residual Volume	SAF-Ext	
14.3.6.1	Total IPSS score	SAF-Ext	
14.3.7.1	Physical Examination Shift from Baseline	SAF-Ext	

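### The Week 52 categorical vital-sign table (SAP Table 14.3.4.3) has an empty 28-week column, because that group's final visit is labelled Week 28

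*SAP*

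**What the plan says.** SAP 7.5 lists extra tables for changes in systolic pressure, diastolic pressure and pulse rate. One counts the subjects in each group with "at least a 5/10/15 CFB at 2 consecutive post-baseline visits and at Week 52 will be produced for all subjects", and then again by hypertension category. In the list of output tables (SAP 11.1.1) the final-visit part is Table 14.3.4.3, titled "Vital Sign Parameter Change from Baseline Shifts at Week 52", on SAF-Ext. Under SAP 3.1.2 that set includes men from both parent-study arms. SAP Table 1 (4.2.1) lists three safety columns: 52 weeks, 28 weeks, and "Overall Vibegron 75 mg Demographic and baseline data, Safety".

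The visit labels are set elsewhere. SAP 3.1.2 says that "all analyses by visit will index visits from the first dose of vibegron on either study" and that "subjects who received placebo in study URO-901-3005 will only contribute safety data up to Week 28". SAP 4.2.4.2 applies its slotting rules "For all non-diary safety data including safety laboratory, vital signs, and PVR volume to be summarized by visit". The last row of Table 4 there reads "Week 52 Visit 14 365 > Day 309 NA NA NA": the first entries belong to the vibegron arm and the three NA entries to the placebo arm.

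SAP 7.8 deals with the same labels for IPSS total score by naming the second group's own visits, "baseline, Week 12 and Week 28 for the 28-week treatment group". SAP 6.2.2.3 does likewise for the PGI. SAP 7.5 has no such statement.

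**The concern.** The table is specified for both groups at a time point that only one of them has. A programmer following 3.1.2 and Table 4 finds no Week 52 record for any former placebo subject. Percentages use the number of subjects with available data (SAP 4.2.2), so the Overall percentages would equal those of the 52-week group while carrying the label of the whole vibegron population.

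The missing data exist. The Schedule of Assessments (Protocol 1.3) has vital signs taken at Visit 14 for every continuing man. Long-term safety is the primary objective and hypertension is a predefined event of special interest. At stake is the categorical blood-pressure and pulse result at the final visit for men with 28 weeks of exposure. No other planned vital-sign table gives it.

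**Working it through.** **1. Label of the final visit in each group**

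Inputs, from Table 4: Visit 14 has nominal Day 365 in both arms. The former placebo group starts vibegron at about the Week 24 visit, nominal Day 169.

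- Former placebo group: (365 − 169) / 7 = 28 weeks on vibegron.
- Its two earlier visits: (197 − 169) / 7 = 4 weeks and (253 − 169) / 7 = 12 weeks.

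These agree with the placebo columns of Table 4, where Visits 12, 13 and 14 are Weeks 4, 12 and 28. The window for Visit 14 has no upper limit, so later records also go to Week 28. No record from this group can be slotted to Week 52.

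**2. The plan's own completer figure**

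Inputs, from SAP 1.2.4: about 300 enrolled, about 33% dropout, 100 completing one year on vibegron. The split between groups is not stated. Completers = 300 × share × (1 − 0.33).

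| Assumed share in the 52-week group | Completers |
|---|---|
| 1/3 | 67 |
| 1/2 | 100.5 |
| 2/3 | 134 |
| 1 | 201 |

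Of these shares, only one half reproduces the stated 100. Equal groups of about 150 are therefore implied, though not written.

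**3. Contributors to Table 14.3.4.3**

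- As written: 150 × 0.67 = 100.5 from the 52-week group and 0 from the 28-week group. The Overall n is also about 100.
- With the 28-week group shown at Visit 14: a further 150 × 0.67 = 100.5, if its dropout is also 33%. The total is 201.
- Omitted share of completers: 100.5 / 201 = one half.

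If the 52-week share is varied over an assumed 45% to 55%, the 28-week group has 165 to 135 men. The omitted completers are then 165 × 0.67 = 111 down to 135 × 0.67 = 90. With equal groups, each percentage point of difference in the 28-week group's dropout moves the count by 150 × 0.01 = 1.5 men.

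**4. What the missing column would show**

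For an assumed 10% of men above a threshold and n = 100, the 95% half-width is 1.96 × √(0.10 × 0.90 / 100) = 5.9 percentage points. With no events, the one-sided 95% upper bound is 1 − 0.05^(1/100) = 3.0%. As written, the 28-week group gets no estimate in this table.

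**The case against.** Several points count against a stronger claim.

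- **All subjects.** A reader might infer that the sentence promises a Week 52 value for every man. In context the phrase heads a list of splits by hypertension category, so it most naturally means not split by that category. This stands. The mismatch rests instead on the counts being planned in each group, on SAF-Ext, with 28-week and Overall safety columns.
- **Dropping out of the blood-pressure assessment.** A reader might infer that half the safety population is lost from it. The documents do not support this. SAP 7.5 keeps the 28-week group in the by-visit summaries to Week 28, the maximum post-baseline change, the continuous change to end of treatment and the listing. It also stays in the consecutive-visit counts. The text there says two visits and the title of Table 14.3.4.2 says three, but the group has three post-baseline clinic visits and can contribute either way. Hypertension adverse events are summarised for both groups. Protocol 9.4.2 asks only for descriptive vital-sign summaries, so this table is supplementary.
- **A 52-week-only table may be intended.** The sample size rests on one-year completers, and 3.1.2 openly stops the other group at Week 28. This is plausible, but the plan does not say so and still calls for three columns.
- **A hidden omission.** SAP 4.2.2 requires N and n, so an empty column and an Overall n equal to the 52-week n would be visible.
- **Week 52 may mean the parent-study week.** SAP 7.5 itself uses parent-study labels for the telephone visits, and on that reading nobody is lost. It conflicts with 3.1.2 and Table 4, and it would pool 28 and 52 weeks of exposure under one label. The text needs a sentence on either reading.
- **The IPSS precedent.** SAP 7.8 lists visits by group and defines no combined end-of-treatment point. It supports a group-specific time point, not a pooled one.

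**Conclusion.** The mismatch is real and follows from the SAP's own rules. As written, Table 14.3.4.3 has an empty 28-week column and an Overall column identical to the 52-week group. About 100 of about 200 expected completers are absent from it, or about 90 to 111 if the 52-week share is 45% to 55%. These counts assume near-equal groups, which the stated sample-size figures imply but the documents do not say, and equal dropout.

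The effect is minor. It is confined to the final-visit categorical table, which is descriptive and carries no test. The thresholds should be quoted as 5/10/15 without a unit, since the SAP gives none and the table includes pulse rate.

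**What to change.** In SAP 7.5, state that the final-visit time point for this table is Week 52 for the 52-week group and Week 28 (Visit 14) for the 28-week group. Show the two groups separately. Drop the Overall column, or label it as mixing 28 and 52 weeks of exposure. Retitle Table 14.3.4.3 to match. If a 52-week-only table is what the sponsor wants, say so and remove the other two columns.

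The populated column also needs one baseline. SAP 1.1 and 3.1.2 take the last value before the first vibegron dose, while 4.3.4 takes the last value before the first double-blind dose. For former placebo subjects these differ, so the sections should be reconciled at the same time.

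The cost is a sentence, a title and one more populated column, with no new data. The drawback is that any Overall column would combine two exposure durations, which is why separate presentation is preferable.
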